### Data Collection (Measures, Time-points and Location)

Measures	Time- Points				
	Immediate Postop	At 24 hours Postop	At 48 hours Postop	At 72 hours Postop	At 03 Months Postop
1. Quantitative Study					
a. The number of early vascular complications identified (incidence).	X	X	X	X	
b. The period between the graft implantation and diagnosis of vascular complication (early or late).	X	X	X	X	
c. The number of departmental ultrasound scans requested in the first 24, 48, and 72 hours postoperatively.	X	X	X	X	
d. The 03-month kidney graft survival					X
2. Qualitative Study					
Exploring the views of stake holders regarding				X	
a. Experience with the intervention				X	
b. participating in the study, and				X	
c. acquiring their suggestions to improve the design of definitive future RCT				X	
Location	Operation theatre recovery	Ward	Ward	Ward	Clinic

## 21. INTENTION TO TREAT ANALYSIS

The data of the participants who will be randomised into the two groups (i.e. Intervention Group and Control Group) will be summarised separately in their respective groups. This method preserves the benefits of randomisation and prevents confounding factors (i.e. non-compliance, missing outcomes, losses to follow up, etc.).

## 22. DATA ANALYSIS

It is inappropriate to use inferential statistics in feasibility study data to formally test the effectiveness of an intervention. Data analyses using descriptive statistics will be performed in IBM SPSS version 25.0. The means and standard deviations will be

considered as the representative value of the continuous variables (i.e. participant's demographic characteristics) . The categorical variables (i.e. surgical outcomes) will be expressed by frequency distributions (percentages) and elaborated using tables and graphs .

The outcomes for each objective in both groups (i.e. intervention and control) will be summarised using descriptive statistics. The numerical data from both groups will be compared to describe the feasibility of the intervention and generate realistic estimates of important parameters for the definitive multi-centre RCT.

### **22.1. PARTICIPANT'S DEMOGRAPHIC CHARACTERISTICS**

The participant's demographic or baseline characteristics in both groups will be summarised separately using descriptive statistics. The numerical data for both groups will be compared in the tabular form to demonstrate whether or whether not the participant's baseline characteristics in the Intervention and Control groups are identical.

**22.2. OUTCOME MEASURES FOR OBJECTIVE 1:** To assess the capability of vascular monitoring device in the early postoperative care of kidney transplant patients.

The first step will be to evaluate if the vascular monitoring device truly works in the sense of achieving its intended outcome (i.e. vascular monitoring in kidney transplant patients). According to the MRC Framework assessing a clear theoretical basis for the intervention is paramount for further evaluation of complex interventions . The percentages of the surgical outcomes in the Intervention and Control groups will be compared in tabular form. From this comparison, it will be noted whether the vascular monitoring device can safely identify vascular complications and prevent graft loss.

The relative risk or risk ratio for the surgical outcomes will also be calculated using the following formula.

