#### 4. STUDY SUMMARY

Study Title	The role of an implantable Doppler vascular monitoring device in kidney transplant patients: a feasibility randomised controlled trial with an embedded qualitative study.
Short title/acronym	Continuous Implantable Doppler probe monitoring in renal transplant (CONDOR Study)
Study Settings	Southwest transplant centre at Derriford Hospital, University Hospitals Plymouth NHS Trust
Study Design	Feasibility randomised controlled trial with an embedded qualitative study
Study Aim	To evaluate the feasibility of an implantable continuous vascular monitoring device in kidney transplant patients and to inform the protocol development of a definitive RCT.
Study Objectives	
Objectives “1-3” will be met within the feasibility randomised controlled trial:
 
 
1. To assess the capability of vascular monitoring device in the early postoperative period of kidney transplant patients.
 
2. To assess the research methods used to compare vascular monitoring device with the standard care and to estimate surgical outcome measures essential to inform the sample size calculation for the definitive planned RCT.
 
3. To assess the availability of research resources, management support, potential barriers and challenges for the definitive planned RCT.
 
 
Objectives “4” will be met within the embedded qualitative study:
 
 
4. To assess the acceptability of vascular monitoring device in clinical practice and to acquire suggestions and innovative ideas of the stakeholders on refining the design of definitive RCT, functioning of the implantable vascular monitoring device, and improving postoperative patient care.
 

Trial Participants	50 kidney transplant patients (25 in the intervention and 25 in the control group)
Inclusion criteria	
 
• Patients who will have deceased or living kidney donor transplants at the Southwest Transplant Center.
 
• Patients aged 18 years or above.
 
• Patients able and willing to comply with the trial requirements.
 

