## **7.0. AIM OF THE STUDY**

To evaluate the usefulness of an implantable continuous vascular monitoring device in kidney transplant surgery and to inform the protocol development of a definitive planned RCT.

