## **18. TRIAL ARMS**

### **18.1. INTERVENTION GROUP (KIDNEY TRANSPLANT PATIENTS WITH THE IMPLANTABLE CONTINUOUS VASCULAR MONITORING DEVICE)**

The intervention that is intended to be investigated is the implantable continuous vascular monitoring device manufactured by COOK Medical Company. Its principle intended use is continuous monitoring of the graft perfusion (i.e. transplanted kidney) for the first 72 hours postoperatively. The kidney transplant patients in the intervention group will receive implantable continuous vascular monitoring device surveillance for the first 72 hours in addition to the standard care clinical observation as part of their postoperative care.

The continuous audible Doppler signals produced by the monitoring device represent the blood flowing in the renal artery. This is an indicator of graft perfusion. Cessation of audible Doppler signals is the key that may suggest hampered blood flow due to vascular complications. In the intervention group, the monitoring device will be used as an added mechanism to monitor graft perfusion. Theoretically, the vascular complications should be identified early, the patients should undergo prompt surgical correction, and better outcomes with less graft loss should be noted in the intervention group as compared to the control group. This scientific basis of the intervention will be tested in this study.

The audible Doppler signals representing the graft perfusion will be monitored continuously by the transplant surgeon till the wound closure in the theatre. In the recovery, the signals will be monitored continuously by the duty nurse till the time patient is transferred to the ward. After that, it will be monitored intermittently as required by the clinician on call in the ward.

The vascular monitoring device is already in use at our hospital by the plastic and reconstructive surgery department, so we do not anticipate any administrative problems with the use of this device. The host renal ward has already trained the nurses and funds have already been allocated to acquire the monitoring devices for the duration of the study. The removal of the monitoring device is a simple and uncomplicated procedure. It will be undertaken 72 hours postoperatively by the duty nurse looking after the patient.

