#### **Risk difference:**

$$\% \text{ in Intervention Group} - \% \text{ in Control Group}$$

By doing so we will note if any substantial change in the outcome of the Intervention Group is observed as compared to the control group. Inferential statistics would be valuable in this regard however they will not be applied due to the study design .

**22.3. OUTCOME MEASURES FOR OBJECTIVE 2:** To assess the research methods used to compare vascular monitoring device against the standard care and to estimate surgical outcome measures essential to inform the sample size calculation for the definitive planned RCT.

The research process assessment will be measured by the selected outcomes. It will determine the suitability of the study methods and procedures adopted in this feasibility study. The outcomes will generate realistic estimates for the definitive multi-center RCT (i.e. eligibility,

recruitment, consent, follow-up rates, etc.). Any limitations or inadequacies will be highlighted for improvement in the latter.

**22.4. OUTCOME MEASURES FOR OBJECTIVE 3:** To assess the availability of research resources, management support, potential barriers and challenges for the definitive planned RCT.

The availability of the research resources and management support in this feasibility study will be evaluated by the selected outcomes. Any limitations or inadequacies will be highlighted for improvement in the definitive multi-center RCT.

The results of the data analysis will be following the CONSORT updated guidelines for reporting feasibility and pilot trials .

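### Section 22.2 would note from 25-versus-25 percentages, with no interval, whether the device prevents graft loss; the expected losses per arm are too few to say

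*Protocol*

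**What the plan says.** Protocol Section 22.2 (analysis for Objective 1) compares the percentages of surgical outcomes by arm in a table and continues: "From this comparison, it will be noted whether the vascular monitoring device can safely identify vascular complications and prevent graft loss". It adds a risk ratio and a risk difference, both as point values, so that "we will note if any substantial change in the outcome of the Intervention Group is observed". No threshold for substantial is given. The next sentence reads: "Inferential statistics would be valuable in this regard however they will not be applied due to the study design".

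The opening of Section 22 takes a different position: "It is inappropriate to use inferential statistics in feasibility study data to formally test the effectiveness of an intervention". It limits the work to descriptive statistics and to estimates of parameters for the definitive trial.

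Section 18.1 sets out, in a sentence that opens with the word theoretically, that "better outcomes with less graft loss should be noted in the intervention group as compared to the control group". It then adds: "This scientific basis of the intervention will be tested in this study".

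The graft outcome is worded in two ways. Section 20.2(d) counts grafts lost to vascular causes within three months. The Section 4 summary and the data collection table in Section 20 give only three-month graft survival, with no cause.

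The document filed as the SAP is a data management plan. It mentions descriptive and analytical statistics but specifies no interval or other method.

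**The concern.** The protocol sets aside the tools for judging effectiveness but keeps a sentence about effectiveness. Whether a device prevents graft loss is a causal conclusion. A table of percentages from 50 patients, with nothing to show their precision, is a poor basis for it when the event is rare.

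This matters because the results are meant to travel. Section 36 says they will inform local practice and be shared with transplant units across the UK. Section 20.3(g) feeds them into the sample size of the definitive trial. Section 25 already lists better graft survival among the possible roles of the device. A table showing 0% against 4% could be read as a signal when it is one patient, and a table showing 0% against 0% could be read as no benefit when almost nothing could have been seen.

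**Working it through.** **Inputs**
- Arm size: 25 and 25 (Section 15). No alpha, power, effect size or precision target stands behind this number, so there is no planned figure to reproduce.
- Graft loss in the first three months: 7-10% (Section 6.2).
- Vascular share of that loss: 30-35% (Section 6.2). Section 6.2 also gives a 20% share, but for 30-day losses.
- Assumptions: these background rates apply at this centre, and all 25 patients per arm are followed to three months.

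**Expected losses per arm if the device has no effect**
- Vascular-cause, as in Section 20.2(d): 0.07 × 0.30 = 2.1% to 0.10 × 0.35 = 3.5%. Times 25 gives 0.525 to 0.875.
- All-cause, as Section 4 and the Section 20 table could be read: 25 × 0.07 = 1.75 to 25 × 0.10 = 2.5.
- Sensitivity, assuming the 20% share also holds at three months: 1.4-2.0%, or 0.35 to 0.5 per arm.

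**Chance patterns with no effect.** Each arm is Binomial(25, p).
- Control arm with no losses, so risk ratio undefined: (1 - p)^25.
- Both arms with none: the square of that.
- Device arm with fewer losses: (1 - S)/2, where S is the sum over k of P(k)², the probability that the arms tie.

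| Reading | p | S | Device arm fewer | Control arm has none | Both have none |
|---|---|---|---|---|---|
| Vascular-cause | 2.1% | 0.452 | 27% | 59% | 35% |
| Vascular-cause | 3.5% | 0.335 | 33% | 41% | 17% |
| All-cause | 7% | 0.228 | 39% | 16% | 3% |
| All-cause | 10% | 0.191 | 40% | 7% | 0.5% |

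At 1.4-2.0%, the device arm has fewer losses in 22-27% of trials and the control arm has none in 70-60%.

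**The other direction.** Suppose, as an assumption, that the device prevented every vascular loss. The table would still show 0 against 0 vascular losses whenever the control arm has none, which is 59-41% of trials at 2.1-3.5%.

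**Precision of results the trial could produce**
- 0/25: the exact upper 95% limit is 1 - 0.025^(1/25) = 13.7%.
- 0/25 against 1/25: difference -4 points. The Wilson limits are 0 to 13.3% and 0.7 to 19.5%. Newcombe lower limit: -0.04 - (0.195 - 0.04) = -0.195. Upper limit: -0.04 + √(0.133² + 0.033²) = +0.097. So about -20 to +10 points.
- 0/25 against 2/25, where the control count lies within the range expected for all-cause loss: -8 points, Newcombe -25.0 to +6.5.

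These intervals are several times wider than the 2.1-3.5% vascular loss rate that the device is meant to lower.

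**The case against.** The best case for the plan is that it is descriptive and says so. The verb in Section 22.2 is only that something will be noted. There is no threshold, test or decision rule, Section 22 confines the comparison to feasibility and parameter estimates, and Section 25 speaks of a possible role. Most of this stands, and it rules out several stronger readings that a reader might infer:

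- *That the plan commits the sponsor to an effectiveness claim, or that 27-33% is a false-claim rate.* Nothing in the plan turns fewer losses into a finding of prevention. The percentages above are chance patterns only.
- *That Section 18.1 predicts less graft loss in this trial.* That sentence is framed as theory. Only the follow-on statement that this basis will be tested here goes too far.
- *That leaving out hypothesis tests is a fault.* It is reasonable for a feasibility trial.
- *That the risk ratio will usually fail.* The 59-41% applies to vascular-cause graft loss only. It drops to 16-7% for all-cause loss. The ratio is also planned for other surgical outcomes, such as vascular complications, whose incidence the documents do not give, and the risk difference is always defined.

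What the objection does not remove is the sentence itself. Describing counts by arm is a description; noting whether the device can prevent graft loss is not. The promise in Section 22.4 to follow CONSORT reporting guidance neither deletes that sentence nor specifies an interval.

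A second objection is that intervals are inferential and so excluded. The bar in Section 22 is tied to formally testing effectiveness, which an interval shown as precision does not do. The later sentence in Section 22.2 is unqualified, however, so it must be amended if intervals are added.

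**Conclusion.** The concern holds as a matter of wording and missing precision. Section 22.2 says that percentages from 25 against 25 will show whether graft loss is prevented and whether there is a substantial change. The plan gives no interval and elsewhere disclaims testing effectiveness. The counts cannot carry the statement under either definition of graft loss: about 0.5-0.9 expected losses per arm for vascular cause, 1.75-2.5 for all causes.

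The expected counts are derived here; the protocol does not state them. They rest on the Section 6.2 rates applying locally and on complete follow-up; dropout would lower them. The conclusion does not depend on which reading is chosen, because the intervals are wide in both. This should be fixed. The design is not in question, and the remedy is small.

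**What to change.** 1. **Section 22.2.** Replace the prevention and substantial-change sentences with wording such as: *Vascular complications found, time to diagnosis, scans requested and graft losses will be described by arm, and device-related problems (20.4e) will be listed, in order to describe whether the device can detect vascular complications. No conclusion about effectiveness or the prevention of graft loss will be drawn from this trial.* This keeps an assessment for Objective 1.
2. **Sections 18.1 and 25.** In 18.1, remove the statement that this basis will be tested here and leave less graft loss as the hypothesis for the definitive trial. Bring the reference in Section 25 to improved graft survival into line.
3. **Intervals.** For 20.2(a) and 20.2(d), report n/N with an exact 95% interval per arm, and the planned risk difference with a 95% interval suited to small counts, such as Newcombe. Report the risk ratio as not estimable when the control arm has no events. Replace the sentence excluding inferential statistics with: *No hypothesis tests will be done; 95% confidence intervals are given to show precision only.* Without this change the plan would contradict itself.
4. **Graft-survival wording.** Reconcile Section 4 and the Section 20 table with 20.2(d), or report both all-cause and vascular-cause loss. Three-month graft survival is already collected.

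The cost is rewording and a few lines of analysis. Recruitment, allocation and data collection stay as they are. The drawback is that the claims become more modest and the intervals will be visibly wide. Even pooled, 2/50 is 4% with an exact 95% interval of 0.5-13.7%, so the definitive trial will also need an event rate from outside this study.

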### 20.1. PARTICIPANT'S DEMOGRAPHIC CHARACTERISTICS

- a. Age at the time of operation in years and months (not the date of birth), gender, and BMI.
- b. Cause of renal deterioration.
- c. Dialysis modality at the time of transplantation
- d. Time on the kidney transplant waiting list
- e. Source of the donated kidney (living versus deceased donor)
- f. Prior renal transplant
- g. Surgeon undertaking the procedure (coded to maintain anonymity)
- h. Recipient risk factors for transplant surgery (age > 70 years, BMI > 30, cardiovascular disease, smoking, peripheral vascular disease, thromboembolic disease, hypertension (HTN), diabetes mellitus (DM), and urological obstructive symptoms)
- i. Donor risk factors for transplant surgery (Donor age > 60 years, BMI > 30, cardiovascular disease, smoking, peripheral vascular disease, hypertension (HTN), diabetes mellitus (DM), cold ischemia time (CIT), cause of death, HLA mismatch, and the number of vessels on the graft).

**20.2. OUTCOME MEASURES FOR OBJECTIVE 1:** To assess the capability of vascular monitoring device in the early postoperative care of kidney transplant patients.

- a) The number of early vascular complications identified and their management (incidence).
- b) The period between the graft implantation and diagnosis of vascular complication (early or late).
- c) The number of departmental ultrasound scans requested by the clinicians taking care of the patients in the first 24, 48, and 72 hours postoperatively.
- d) The 03-month kidney graft survival (the number of grafts lost due to vascular complications in the first 03 months).

**20.3. OUTCOME MEASURES FOR OBJECTIVE 2:** To assess the research methods used to compare vascular monitoring device with the standard care and to estimate surgical outcome measures essential to inform the sample size calculation for the definitive planned RCT.

- a. Suitability of eligibility criteria and recruitment process.
- b. Refusal rates for participation and randomization
- c. Retention and follow-up rates during the research process

- d. Assessment of the study methods, procedures, and follow-up schedules (researcher and participants)
- e. Assessment of the procedures for monitoring variation and fidelity in the delivery of the intervention. A fidelity checklist will evaluate the adherence to the standardised protocol of intervention delivery (i.e. consent of the participants, delivery of the intervention, and conduct of the serial Doppler signal monitoring).

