- f. Assessment of the feasibility, appropriateness and performance of the potential outcome measures for the definitive multi-centre RCT.
- g. Calculation of the means and standard deviation of the outcome measures arising from the differences between the intervention and control arm essential to inform sample size calculation for the definitive planned RCT.

**20.4. OUTCOME MEASURES FOR OBJECTIVE 3:** To assess the availability of research resources, management support, potential barriers, and challenges for the definitive planned RCT.

- a) Assessment of ease and simplicity of the participant documentation (i.e. participant information sheet, consent form, data collection sheet) through the study
- b) Availability of equipment and medical staff in the host centre to handle the number of participants and the research procedures
- c) Technological capacity for communication and adequate software to randomize, record, process, and store research data.
- d) Availability of management support for the research project and back up plans for any extenuating circumstances.
- e) Documentation of any technical glitches or postoperative complications related to application of the monitoring device.
- f) To explore factors that will enable future economic evaluation of the vascular monitoring device in the definitive planned RCT (i.e., testing procedures that can collect information to inform a cost effectiveness analysis).

Data will be collected by the chief investigator using a standardised proforma in the Microsoft Office Excel Database (Microsoft Corporation, San Jose CA, USA). All collected data will be pseudonymised using unique anonymised codes. It will be kept strictly confidential and will not contain any participant identifiers.

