### 37.2 REPORTING OF AE

All AE's occurring during the study observed by the investigator or reported by the participant, whether or not attributed to the device under investigation will be recorded on the CRF. All ADE's will be recorded in the CRF.

The following information will be recorded: description, date of onset and end date, severity, assessment of relatedness to device, other suspect drug or device and action taken. Follow-up information should be provided as necessary.

The relationship of AEs to the device will be assessed by a medically qualified investigator or the sponsor/manufacturer and will be followed up until resolution or the event is considered stable.

All ADE that result in a participant's withdrawal from the study or are present at the end of the study, should be followed up until a satisfactory resolution occurs.

**Where relevant**, any pregnancy occurring during the clinical study and the outcome of the pregnancy should be recorded and followed up for congenital abnormality or birth defect.

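### Section 22.2 will judge whether the device works safely from outcomes that capture harm only in part, while the adverse events recorded under 37.2 are never summarised by arm

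*Protocol*

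**What the plan says.** Section 22.2 (Objective 1) sets the comparison: "The percentages of the surgical outcomes in the Intervention and Control groups will be compared in tabular form". It then says that from this comparison "it will be noted whether the vascular monitoring device can safely identify vascular complications and prevent graft loss". A risk ratio and a risk difference follow, with no inferential statistics.

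Section 20.2 lists the four Objective 1 outcomes: (a) early vascular complications and how they were managed; (b) time from implantation to diagnosis; (c) "The number of departmental ultrasound scans requested by the clinicians taking care of the patients in the first 24, 48, and 72 hours postoperatively"; and (d) 3-month graft survival, defined as the number of grafts lost to vascular complications.

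Safety information appears in two other places. Section 20.4(e), under Objective 3, lists "Documentation of any technical glitches or postoperative complications related to application of the monitoring device". Section 37.2 requires all adverse events, "whether or not attributed to the device under investigation will be recorded on the CRF". Section 22 says that the outcomes of each objective will be summarised in both groups, but 22.1 to 22.4 name no summary of AEs, SAEs or device effects. The document supplied as the SAP is a data management plan and adds none.

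**The concern.** The word safely in 22.2 is tied to a named comparison, so it works as an analysis rule. The comparison it names was built to show detection and graft salvage. It sees only part of the harm that a probe placed around the renal artery could do, and the data that would show the rest have no planned use.

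The Protocol is also inclined to read a quiet record as reassurance. Sections 28 and 37.5 report no device problems at the Trust so far, and Section 25 expects the results to speak to patient safety. A statement that the device worked safely, resting on 22.2 alone, could be carried into the case for the definitive trial without an overall comparison of adverse events between the randomised groups.

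**Working it through.** No safety rate, margin or precision target is stated, so there is no figure of the plan's own to reproduce. The check sets the sections side by side and then looks at how much 25 patients per arm can show.

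**Step 1. Device risks in 37.5 against the Objective 1 outcomes in 20.2.**

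| Risk listed in 37.5 | Seen by Objective 1? |
|---|---|
| Vessel perforation or laceration | In part: under (a) if counted as an early vascular complication, under (d) if the graft is lost |
| Infection | No |
| Erosion, implant rejection | Only if it presents as a vascular complication |
| Dislodgement or migration | No |
| Crystal separation, or crystal that cannot be removed | No |
| Loss of signal | Indirectly, through extra scans in (c) |

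**Step 2. Can (a) and (d) be read as safety?** The count in (a) rises if the probe finds complications that would otherwise be missed. It also rises if the probe causes them. A difference between arms in either direction therefore does not separate the two. Outcome (d) is a clear harm, but it leaves out grafts lost for any other reason.

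**Step 3. Where the recorded adverse events go.** The 37.2 requirement is not limited by arm or by relatedness. AEs are not an outcome under any objective, so the general promise in Section 22 to summarise each objective's outcomes does not reach them. Objective 3(e) is reached by that promise, but an event defined as related to the device cannot occur in a control patient. The control count is zero by definition, and the difference between arms is not a treatment contrast. Relatedness is also judged without blinding (Sections 19 and 37.2). The Objective 3 analysis text in 22.4 speaks of resources and management support and does not mention complications.

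**Step 4. How much information outcome (d) carries.** Inputs from Section 6.2: early graft loss 7% to 10%, of which 30% to 35% is vascular. From Section 15: 25 per arm.

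- Vascular graft loss: 0.07 × 0.30 = 2.1% to 0.10 × 0.35 = 3.5%.
- Expected losses per arm: 25 × 0.021 = 0.5 to 25 × 0.035 = 0.9.
- Chance of none in one arm: (1 − 0.021)^25 = 59% to (1 − 0.035)^25 = 41%.
- Chance of none in either arm, at the same rate in both: (1 − 0.021)^50 = 35% to (1 − 0.035)^50 = 17%.

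**Step 5. How much an adverse event table could show.**

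- Zero events in 25: upper limit 1 − 0.05^(1/25) = 11.3% (one-sided 95%) or 1 − 0.025^(1/25) = 13.7% (two-sided 95%, exact).
- One event in 25: exact 95% interval 0.1% to 20.4%.
- Chance of at least one event among 25 device patients, 1 − (1 − p)^25: 22%, 40%, 72% and 93% for p = 1%, 2%, 5% and 10%. These rates are assumptions; the documents give no adverse event rate.

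Steps 1 to 3 establish the gap. Steps 4 and 5 show that neither the present outcomes nor the added table can establish safety at this size. That limit should be stated with the results.

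**The case against.** A reader might infer that none of the four outcomes measures safety, or that the trial could call the device safe without comparing a single adverse event between arms. The documents do not support either reading. Vascular complications and lost grafts meet the AE definition in 37.1.1, and those needing surgery to prevent permanent impairment meet the SAE definition in 37.1.3. Section 22.2 compares them by arm. The fair criticism is partial coverage.

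A reader might also take the absence of an adverse event row from the data collection table in Section 20 as evidence that these events are not collected. That is weak evidence. The table's quantitative rows are Objective 1 only, Objectives 2 and 3 have no rows either, and 37.2 requires recording throughout the study. The gap is in analysis, not collection.

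Three further points stand in part:

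- Section 22.2 says only that something will be noted, in a plan that rules out formal testing. That softens the sentence but does not change the evidence it rests on.
- The 11.3% and 13.7% limits are correct but do not measure the defect. They are the same after the fix, because 25 per arm does not change.
- On false alarms, Section 6.3 describes re-exploration if the patient is still in theatre and confirmatory imaging once on the ward, so part of that burden would appear in the scan count. A return to theatre that finds nothing is still not an Objective 1 outcome, nor is it a named field in 37.2.

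Sections 37.3 and 37.4 provide prompt reporting to the sponsor and yearly safety reports. These are oversight steps and specify no by-arm summary.

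**Conclusion.** The concern holds in this form: 22.2 promises a statement on safety from outcomes that cover listed device harms only in part, and no by-arm summary is planned for the adverse events that would fill the gap. It should be corrected. It does not threaten the feasibility objectives, the randomisation or the collection of data.

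In size, the one unambiguous harm among the Objective 1 outcomes is expected 0.5 to 0.9 times per arm, with a 17% to 35% chance of no occurrence in the whole trial. This assumes that the background rates in Section 6.2 apply at this centre and are equal in both arms. A count of zero in 25 would still be compatible with a true rate of up to 13.7%. The conclusion about the missing summary rests on the text alone and on no assumed rate.

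**What to change.** 1. In Section 22, add a descriptive by-arm table from the 37.2 CRF data to 3 months: participants with at least one AE and with at least one SAE, as n, % and risk difference. An exact 95% interval is preferable, labelled as descriptive; used that way it does not test effectiveness and so does not conflict with Section 22.
2. Beside it, give counts of ADEs and SADEs in the device arm only, without presenting them as a comparison.
3. Where the recorded action taken allows, identify unplanned returns to theatre in both arms.
4. State that AE recording covers control participants. One explanatory sentence in 37.1.1 is phrased around use of the device and could be read otherwise.
5. In 22.2, delete the word safely or tie it to this table, and add that 25 per arm cannot establish safety (0/25 leaves a two-sided 95% upper limit of 13.7%).

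An adverse event row in the Section 20 table would help clarity but is optional. The cost is one extra output table from data already required, one edited sentence and a more cautious safety statement. Item 3 may be incomplete, because return to theatre is not a separate CRF field under 37.2.
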